Describe the DSMB including frequency of meetings, members, data reviewed, and stopping points.

Click or tap here to enter text.

 \Box The study will have a DSMP.

Describe the DSMP, including what data or responses are monitored, when data is reviewed, and what actions are taken to react to a safety concern.

Required Consent Disclosures						
Child and Elder Abuse						
Texas law requires that anyone report suspected child/elder abuse or neglect.						
Is it likely investigators could		Yes, it is likely.				
discover information that		Include mandated reporting language in applicable informed				
would require mandatory		consent document(s).				
reporting by the investigators	\boxtimes	No, it is not likely.				
or staff?						

Incide	Incidental Findings					
	ental findings include: genetic markers, concerning test results, disease, suicidal thoughts, bected paternity, engaging in illegal activities.					
\boxtimes	It is possible that investigators could discover incidental findings or other information					
	about a participant's previously unknown condition.					
	If so, state methods for addressing and reporting incidental findings					
	Issues of concern that would be identified by Meals on Wheels volunteers during their typical					
	process of meal delivery may be identified during calls with the Meals on Wheels clients, such					
	as missing meal deliveries or prescription access needs. We will use the same process to share					
	issues that has been developed by Meals on Wheels for their volunteer meal deliverers					
	Include incidental report information as applicable in the informed consent document(s).					

41

Early Withdrawal

List the criteria for withdrawing individual participants from the study (*e.g.*, safety or toxicity concerns, emotional distress, inability to comply with the protocol, or requirements from study sponsor).

Participants may withdraw from the study at any point.

Describe any necessary procedures for ensuring the safety of a participant who has withdrawn early.

None

Describe any pre-specified criteria for stopping or changing the study protocol due to safety concerns. *None*

If any of the above are applicable, include this information in your consent form.

42

43

PRIVACY AND CONFIDENTIALITY

44

Privacy

Describe how you will protect the identity and privacy of study participants during each phase of research. Privacy focuses on the individual participants rather than data. In this section, researchers should focus on issues such as where research activities take place and how participant involvement is protected from non-participants.

Include information regarding privacy during identification, recruitment, screening, the consent process, the conduct of the study, and dissemination of data.

Identification (via Meals on Wheel staff), screening, recruitment, and the intervention will take place over the phone which will reduce the risk of loss of privacy. All documents, including consent forms, will be kept on secure servers within Dell Medical. Any hard copies of documentation will be stored in locked filing cabinets in controlled-access buildings within Dell Medical

45

Confidentiality and Data Security Plan

Describe how you will protect the confidentiality of data or address confidentiality concerns.					
	Identifiers will be coded to protect confidentiality.	Describe how data is coded and where identifiers are stored.			
	protect connactituity.				
	Identifiable data will be	Describe destruction plan and timeline			
\boxtimes	destroyed.	Identifiable data will be deleted from data and lists at t			
		end of the study.			
	Identifiable data will not be destroyed.	Provide rationale for retaining identifiable data			
		indefinitely.			
	be destroyed.	Click or tap here to enter text			
Describe how you will store and secure your data (including length, location, and medium of					
storage):					
ΔII d	All data will be stored in the Dell Medical School REDCan database. This secure, HIPAA				

All data will be stored in the Dell Medical School REDCap database. This secure, HIPAA compliant database can only be accessed with password and dual authentication

46

Dat	Data Access					
\boxtimes	Study team members 🔲 Collaborators 🛛 Data coordinating center				Data coordinating center	
	Sponsor		Future sharing with	X	Other: Meals on Wheels Central	
	эропзог		other researchers		Texas	
Describe Data Sharing (If Applicable)						
Identifiable research data will be shared outside of the research team, with Meals on Wheels,						
unless the participants give explicit denial to share identifiable data with Meals on Wheels						
post-study. Data sharing with Meals on Wheels would be for the purpose of internal use only						
to better support the care provided to the Meals on Wheels client. This would include						
referral of services suggested by a participant's survey scores. A member of the research						
team will ask specifically if the participants do not want to share data with MOW. Aggregate						
data without identifiers will be shared with healthcare payers, and may be presented in						
pub	public forums					

47

Cer	Certificate of Confidentiality					
See	See IRB Policies and Procedures Section 4.11.5 for a description of a Certificates of Confidentiality.					
X	The study does not require a Certificate of Confidentiality.					
	The study requires a Certificate of Confidentiality.					
	□ NIH has issued a Certificate of Confidentiality for this study.					
		A Certificate of Confidentiality has not been obtained, but there are plans to apply				
		for one.				

COMPENSATION AND COSTS

49								
	Con	npensation						
	\boxtimes	Subjects receive compensation.						
		Subject will not receive co	mpe	nsation.				
	Tot	al amount of compensatior	1	\$10				
			Control group participants will receive a \$10 HEB or Visa gift card upon completion of the post-intervention measurement collection. This will be emailed or mailed to the participant based on their preferred method.					
	Pro	ration schedule		Click or tap	here	to enter text	t.	
		en do subjects receive ipensation?		Click or tap	here	to enter text	t.	
	Sele	ect the form(s) of compensation	ation					
		Cash		Check			\boxtimes	Gift Card \$10 HEB or Visa gift card
		Course Credit		ClinCard				Other: Click or tap here to enter text.
	\boxtimes	Compensation amount an requested of them.	d typ	pe reasonable for this population for the activities				
		We use standards from similar prior approved and completed work						
50		 						
	Cos	ts						
		ect all categories of costs fo	r wh	ich participa	ints d	or their insu	iranc	e companies will be
		ponsible.						
	\boxtimes	Participants will have no c		associated v	with	,		
		Standard of care procedures contributing to study dataResearch procedure standard of care						edures not associated with re
		Administration of drugs /	ces	□ Study drugs or devices			devices	
		Transportation and parking						
		Other: Click or tap here to enter text.						
51		1						
52								

REQUIRED DOCUMENTS

53

Additional Supporting Documents

Principal Investigator CV - Required

Page 24 of 25

	Faculty Sponsor CV – Required for student PIs
\boxtimes	Recruitment Materials
\boxtimes	Consent, Parental Permission, and Assent Forms
\boxtimes	Measures and Instruments
	Sponsor Protocol
	Investigator Brochure
\boxtimes	Personnel Form
	IDE/IND Verification
\boxtimes	Supplemental Forms

54

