Primary outcome: Loneliness as measured by the 6-item De Jong Gierveld Loneliness Scale; secondary outcomes include depression and anxiety. All three outcome measures yield continuously distributed summary scores with interval scale properties; and all three outcomes are measured both prior to and after the intervention period. This design permits us to examine whether the phone-based loneliness intervention differentially improves the loneliness scores over that of the control group. Mixed linear models/ hierarchical linear models will be adopted to model pre to post change in loneliness at level-1; we will test whether the pre to post changes in loneliness differs as a function of treatment assignment at level-2. These analyses will control and test for differences in the magnitude of the treatment effect across the 6 callers at level-2. Participant ratings pertinent to perception of the caller's empathy/impact measured by CARE as part of the sub-study will also be included at level-2. A similar analytic approach will be adopted to test if the phone-based loneliness intervention also affects depression and anxiety ratings from pre to post-intervention. The rank-order stability of loneliness, depression, and anxiety scores tend to be moderate to large; and moderate to high correlations affect statistical power positively. A sample size of 125 participants in each group can detect a small effect size for the interaction of group with pre to post-difference (f=.09 to f=.10) with 80% to 90% power respectively using an alpha of .05 assuming a correlation of .60 between the pre and post measurements. The sample size of 125 participants in each group has been established to adequately power the study to provide information on the effect of the intervention to inform future planned studies. Mixed linear models will permit the estimation of these models when there is missing data while accounting for greater similarity in therapeutic effects in subsets of participants due to shared callers who deliver the intervention. The exploratory analyses pertinent to perception of the impact/approach of the caller by the participant will be incorporated into these primary analyses and will inform whether the perception of effectiveness predicts the magnitude of change from pre to post intervention.

8

Funding and Regulatory Oversight

Check all agencies that fund or hold regulatory oversight over the research activities.						

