Study participants will be randomized after baseline measurement are completed using Redcap randomization functionality and as designed by the statistical team, as a block randomization.

Participants randomized into the control group will be told they are in the second arm of the program, that they will receive a call after 4 weeks (for measurement), and to expect to receive an HEB or Visa gift card after that. In the intervening 4 weeks, they will not receive any additional contact by research team until the post-4-week measurement data is collected.

v. Program Intervention

For those randomized to the intervention arm, the following program elements will be implemented:

The client name and telephone number, will be placed on the caller's call schedule to begin calling on the next business day.

During the first call, the caller will introduce themselves and remind the participant about the program elements. The content of the call will include a question asking how the participant is doing, otherwise the call will be unscripted. The caller will be able to document the call content in the phone system as a reminder of topics shared by the participant for future call continuity. Should an issue that requires sharing with MOW be identified, as pre-determined by MOW case management staff, the caller will forward the

Procedures								
determined by MOW a by MOW. Should an u related to the health a	on the same day. Resolution of t and could potentially result in ad nexpected urgent issue be iden nd safety of the participant, the will reach out to the MOW case e study participant.	ditional services provided tified by the caller that is PI will be contacted via						
frequency of the calls i choice. Requests to re	During the first call of the week for weeks 2-4, the participant will be asked if the frequency of the calls is acceptable, providing the participant with agency and choice. Requests to reduce the frequency of calls to a minimum of two calls per week will be used to adjust the call schedule for the week.							
Each call will last appro	oximately 5 - 10 minutes.							
•	rention arm will receive survey p ing and end of the 4 week study	•						
will only be asked of the partic	ed surveys at the post-4-week p cipants in the intervention arm o tected health information will be ed as part of this study.	luring the post-4 week						
		riequency						
Demographics (Name, Age, Sex, Race, Redcap Survey Baseline Language, Phone number, Address)								

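### The planned group-by-time test of loneliness makes no stated use of the pre-randomisation baseline as a covariate or common mean; on its ordinary reading it uses about 80% of the available information at a correlation of .60

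*Combined protocol and SAP*

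**What the plan says.** The Data Analysis part of Design and Methodology describes the primary model in two steps: "Mixed linear models/ hierarchical linear models will be adopted to model pre to post change in loneliness at level-1"; then "we will test whether the pre to post changes in loneliness differs as a function of treatment assignment at level-2". The outcome is the 6-item De Jong Gierveld score. Depression and anxiety are to be analysed in a similar way, and "all three outcomes are measured both prior to and after the intervention period". The level-2 terms named are treatment, caller and the CARE rating.

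The sample size statement, given there and again in the Total Sample Size table, concerns the same contrast: "A sample size of 125 participants in each group can detect a small effect size for the interaction of group with pre to post-difference". Its inputs are "f=.09 to f=.10) with 80% to 90% power respectively using an alpha of .05", and it is calculated "assuming a correlation of .60 between the pre and post measurements".

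On timing, item iv (Randomization) of the Procedures section says: "Study participants will be randomized after baseline measurement are completed".

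No section names baseline loneliness as a covariate, says that the arms share a baseline mean, or writes out the equation for the level-2 intercept.

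**The concern.** With two time points and complete data, the ordinary group-by-time interaction equals the difference between arms in mean change score. That model lets the two arms have different true baseline means. Here baseline precedes randomisation, so the true means are equal and any observed difference is chance. Estimating a difference known to be zero in expectation adds noise to the treatment estimate.

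At stake is precision on the primary outcome, and on PHQ-8 and GAD-7, from data that the trial already collects. The margin may be needed. The sample size statement gives no allowance for dropout or for clustering by caller, although the Data Analysis section expects both missing data and similarity among participants who share a caller.

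**Working it through.** **Inputs from the documents.** 125 per arm (N = 250); two measurement times; pre-post correlation ρ = .60; alpha .05 (sidedness is not stated; taken as two-sided); f = .09 and .10.

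**1. The plan's own power figure.** For the interaction, λ = f² × N × 2 / (1 − ρ), with 1 and 248 degrees of freedom.
- f = .09: λ = .0081 × 250 × 2 / .40 = 10.1, power 88.7% (stated 80%).
- f = .10: λ = .0100 × 250 × 2 / .40 = 12.5, power 94.1% (stated 90%).

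The stated figures do not reproduce at ρ = .60, and they err on the conservative side. The f values that give 80% and 90% power are .080 and .092. The stated pair is close to what ρ = .50 gives at N = 250 (80.9% and 88.3%), or ρ = .60 at N = 200 (80.9% and 88.2%). The documents state neither combination.

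**2. Variance of the two estimates**, in units of score variance, with complete data, equal pre and post variances and no caller effect.
- Change score: 2(1 − ρ) × 2/125 = .80 × .016 = .0128.
- Baseline-adjusted: (1 − ρ²) × 2/125 = .64 × .016 = .01024.
- Ratio: (1 + ρ)/2 = .80.

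A simulation of 20,000 trials gave .01288 and .01030, a ratio of .800. In sample size terms, 100 per arm with adjustment matches 125 per arm on change. Equivalently, the change analysis would need 250/.80 = 312.5 participants in total to match the adjusted analysis at 250.

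| ρ | Ratio | Loss |
|---|---|---|
| .50 | .75 | 25% |
| .60 | .80 | 20% |
| .70 | .85 | 15% |

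**3. Power and detectable difference at ρ = .60.** With two arms and two times, d = 4f, so f = .09 is 0.36 SD.

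| | Change | Baseline-adjusted |
|---|---|---|
| Power at 0.36 SD | 88.7% | 94.3% |
| Detectable at 80% power | 0.317 SD | 0.284 SD |
| Detectable at 90% power | 0.367 SD | 0.328 SD |

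The change-score values 0.317 and 0.367 SD correspond to f = .079 and .092. They are not the plan's f = .09 and .10.

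**4. With dropout.** Assume that 20% of post scores are missing at random (100 completers of 125 per arm). The likelihood-based variance per arm without the constraint is (1 − ρ²)/100 + (1 − ρ)²/125 = .0064 + .00128 = .00768. The common baseline mean removes the second term. The ratio is .0064/.00768 = .83, a loss of about 17%.

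**5. With caller clustering.** Assume a between-caller variance τ² of .02 to .05 of score variance in the intervention arm. This adds τ²/k for k callers, and baseline adjustment does not reduce it. The Design section gives 4 to 6 callers; the Data Analysis section gives 6.
- k = 6: (.01024 + .0033)/(.0128 + .0033) = .84 at τ² = .02; (.01024 + .0083)/(.0128 + .0083) = .88 at τ² = .05.
- k = 4: (.01024 + .0050)/(.0128 + .0050) = .86; (.01024 + .0125)/(.0128 + .0125) = .90.

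The loss is about 10% to 16%.

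**The case against.** The strongest objection is that the model with free baseline means is an inference. The quoted sentence says only that treatment predicts pre-to-post change, and this would also describe a model in which treatment enters the slope but not the intercept. Such a model already has the efficiency of ANCOVA. This stands as a limit on certainty. The power statement is for the ordinary interaction, which favours the usual reading, but a sample size calculation does not fix the fitted model. What the documents establish is that the baseline specification is not stated.

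A second objection is that 20% is an idealised figure. This also stands. Dropout and caller clustering both reduce it. Unequal pre and post variances could move it either way. The plan's model also carries caller and CARE terms, and the variance of the treatment term in that full model has not been computed.

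A reader might infer that the planned test is biased, or that the trial is underpowered because of it. The documents support neither. Under randomisation the change contrast is unbiased and its test is valid. At ρ = .60 it exceeds the stated power before dropout and clustering. Its sensitivity to a chance baseline imbalance is the same variance loss seen conditionally, not a second defect.

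**Conclusion.** The point holds as an efficiency improvement. If the interaction is fitted in the ordinary way, with baseline means free in each arm, it uses about 80% of the available information at the plan's correlation. That figure assumes complete data, equal pre and post variances and no caller effect. Under the assumptions shown, the loss is about 17% with 20% dropout and about 10% to 16% with caller clustering. If the sponsor already intends a common baseline mean, nothing is lost and only the wording needs completing. In either case the plan should say which model is meant, because its present text leaves the choice open until after the data are seen. Validity is not in question, and no stated power target is missed on this account.

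**What to change.** Add to the Data Analysis section that the primary estimate is the post-intervention treatment difference from the mixed model with a common baseline mean across arms. Treatment enters the time slope only, and the pre/post covariance is unstructured. With complete data, an ANCOVA of the post score on baseline is equivalent and may be named instead. Keep the planned caller terms in the model, and state the same form for PHQ-8 and GAD-7.

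When this is done, restate the power with the correlation actually used, since the stated values do not follow from .60 at N = 250.

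The cost is a sentence or two of specification and, for ANCOVA, one degree of freedom. No extra data, visits or participants are needed, and the mixed model's handling of missing outcomes is kept.

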Randomization: Names of participants who are consented and enrolled in the study will be shared with the research manager who will randomize the participants into either the control or the intervention arm using Redcap randomization functionality. To ensure balance over time, treatment assignment will be block randomized with blocks in random sizes of either four or six, wherein the research associate will be blinded to block and blinded to the next treatment assignment in the randomization list. The statistical team will prepare the randomization model. Participants in the intervention will be added to the caller's call schedule to begin the calls on the next business day.

The intervention arm will include 125 MOW clients to receive a call of between 5 - 10 minutes in length each by a consistent caller, five times a week, Monday through Friday for 4 consecutive weeks to check in on them. After the first week of calls, subjects in the intervention

arm will be asked if the frequency of calls is acceptable or if they would like to reduce the call frequency, potentially to a minimum of twice per week.

- 1. Each caller has between 20-25 participants in a daily panel. 4-6 callers are in the process of recruitment.
- 2. Each call is 5 10 minutes in length.
- 3. The intervention will last 4 weeks for each MOW client.
- 4. Callers will use a telephone system that identifies their calling organization as Dell Med in caller id. Telephone number called, date of call, and length of call will be captured automatically.

Callers: Brief guidance and training will be provided for daily conversation to maximize time spent speaking by the recipient but otherwise the calls are unscripted other than specific prompts to ask about the recipient's general sense of well-being. "How are you doing today?"

Issue Sharing: We will utilize MOW's current process, used by their volunteer food deliverers, to share issues identified during the intervention calls that might result in additional service offered by MOW. Should an unexpected urgent issue be identified by the caller that is related to the health and safety of the participant, the PI will be contacted. The PI will reach out to the MOW case managers to ensure the health and safety of the study participant. Additionally, participants may give permission to share their survey tool results with MOW, in which case, MOW will address concerning survey scores.

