Total Sample Size	Total Sample Size					
Total number of participants for all participant groups	N = 250 for sub-study N = 7					
Sample size rationale	A sample size of 125 participants in each group can detect a small effect size for the interaction of group with pre to post-difference (f= .09 to f= .10) with 80% to 90% power respectively using an alpha of .05 assuming a correlation of .60 between the pre and post measurements. The sample size of 125 participants in each group has been established to adequately power the study to provide information on the effect of the intervention to inform future planned studies.					

SCREENING & RECRUITMENT

24

Identification and Screening

This study involves obtaining information or biospecimens for the purpose of screening, recruiting or determining eligibility of prospective subjects prior to informed consent by either:

- 1. Oral or written communication with the prospective subject or LAR
- 2. By accessing records containing identifiable private information or stored identifiable biospecimens

Describe the identification and/or screening procedures:

Click or tap here to enter text.

25

Rec	Recruitment					
			zed for this research and des	cribe	the recruitment process.	
	oad copies of recruitment		Flyer		In-Person	
	Letter		Social Media		Research Pool	
\boxtimes	Telephone/Text		Snowball sampling		Web-posting	
	Word of Mouth		Other: Click or tap here to	ente	r text.	
Des	scribe the recruitment p	roces	s including where recruit	ment	will take place.	
Describe the recruitment process including where recruitment will take place. MOW staff will call current clients drawing from their information management system. Clients with documented cognitive impairment or in a hospice program will not be called. MOW staff will use a script to introduce the telephone intervention study and seek permission to share the client's contact information. For clients who assent, MOW will forward client names and telephone numbers on to the research team in an Excel spreadsheet using Box, a secure data sharing option, in batches of 25. MOW will continue placing interest calls to clients until such time as they are notified by the research team that the 250 study participants have been consented and enrolled.						

OBTAINING INFORMED CONSENT

28

26 27

Consent Overview	
Select all applicable.	

Page 15 of 25

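### The stated 80% to 90% power makes no allowance for caller clustering that the plan itself expects, and does not follow from its own inputs; whether power falls short depends on a caller ICC the documents do not give

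*Combined protocol and SAP*

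**What the plan says.** The sample-size statement stands in Design and Methodology, Data Analysis, and is repeated in the Total Sample Size table: "A sample size of 125 participants in each group can detect a small effect size for the interaction of group with pre to post-difference". It pairs f = .09 with 80% and f = .10 with 90% power, "using an alpha of .05" and "assuming a correlation of .60 between the pre and post measurements". It gives no caller ICC, design effect, caller count or dropout allowance, and does not state whether the test is one- or two-sided.

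The same Data Analysis paragraph says the mixed models will handle missing data "while accounting for greater similarity in therapeutic effects in subsets of participants due to shared callers who deliver the intervention". It also plans to test whether the treatment effect differs between callers, whom it places at level 2 alongside treatment assignment. It does not say whether callers are fixed or random effects.

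On the number of callers:
- The intervention-arm description says "4-6 callers are in the process of recruitment", with daily panels of 20 to 25 and the same caller for each participant throughout.
- Data Analysis refers to six callers.
- The Total Sample Size table says "N = 250 for sub-study N = 7". The sub-study participants are the primary study's callers.

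The control arm has no callers.

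**The concern.** The plan expects outcomes to cluster by caller and intends to model this, but leaves it out of the power figure. In the intervention arm about 125 people are divided among a handful of callers, roughly 18 to 31 each. If callers differ in effectiveness, the mean change in that arm is less precise than 125 independent observations would make it. The caller variance must also be estimated from only 3 to 6 degrees of freedom.

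The figure matters because the plan justifies 125 per group as adequate to inform later studies. If the trial finds no effect, the result will be weighed against a claimed 80% to 90% chance of detecting one. If the caller ICC is not very small, that claim is too favourable.

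**Working it through.** **Inputs from the documents.** 125 per arm (N = 250), f = .09 and .10, alpha .05, pre-post correlation ρ = .60, and C = 4 to 7 callers in the intervention arm only.

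**Assumptions.** Two-sided test, no dropout, equal panels, random callers, and a caller ICC on the change score of 0 to .05.

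**Step 1: the plan's own figure, independent participants.** For a group-by-time interaction with two measurements, λ = f² × N × 2 / (1 − ρ), on 1 and 248 df.
- f = .09: λ = .0081 × 250 × 2 / .4 = 10.125, power 88.7%.
- f = .10: λ = .0100 × 250 × 2 / .4 = 12.5, power 94.1%.

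The stated 80% and 90% are not reproduced. A one-sided test moves further away (93.7% and 97.0%). Pairs close to those stated come from ρ = .50 (80.9% and 88.3%) or from 200 analysed participants at ρ = .60 (80.9% and 88.2%). The documents state neither.

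**Step 2: the same problem as a comparison of mean change.** In units of the cross-sectional SD:
- The variance of change is 2(1 − .60) = 0.8.
- The difference in mean change is 4f, which is 0.36 or 0.40.
- Each arm mean has variance 0.8/125 = .0064.
- Check: (0.36)² / (2 × .0064) = 10.125, as in Step 1.

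**Step 3: add callers to the intervention arm.**
- Design effect: DE = 1 + (125/C − 1) × ICC. The control arm is unchanged.
- SE = √[.0064 × (1 + DE)], and the noncentrality is 4f/SE.
- Satterthwaite df = (1 + DE)² / [DE²/(C − 1) + 1/124].

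Example with C = 6 and ICC .05:
- DE = 1 + 19.83 × .05 = 1.99, and SE = √(.0064 × 2.99) = 0.138.
- Noncentrality = 0.36/0.138 = 2.60 at f = .09 and 0.40/0.138 = 2.89 at f = .10.
- df = 2.99² / (1.99²/5 + 1/124) ≈ 11.2.
- Power is 66.1% and 75.1% by noncentral t, or 73.9% and 82.4% by normal approximation.

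**Results: power (%) at f = .09 / f = .10**

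| Callers | Method | ICC 0 | ICC .01 | ICC .02 | ICC .05 |
|---|---|---|---|---|---|
| 4 | Satterthwaite | 83.0 / 89.9 | 75.4 / 83.6 | 68.4 / 77.2 | 51.7 / 60.3 |
| 4 | Normal | 88.9 / 94.2 | 84.3 / 90.9 | 79.6 / 87.2 | 67.0 / 76.0 |
| 5 | Satterthwaite | 84.6 / 91.1 | 79.2 / 86.9 | 74.0 / 82.4 | 60.4 / 69.4 |
| 5 | Normal | 88.9 / 94.2 | 85.2 / 91.6 | 81.5 / 88.8 | 71.1 / 79.8 |
| 6 | Satterthwaite | 85.5 / 91.8 | 81.4 / 88.7 | 77.3 / 85.3 | 66.1 / 75.1 |
| 6 | Normal | 88.9 / 94.2 | 85.9 / 92.1 | 82.8 / 89.8 | 73.9 / 82.4 |
| 7 | Satterthwaite | 86.1 / 92.3 | 82.8 / 89.8 | 79.5 / 87.1 | 70.0 / 78.8 |
| 7 | Normal | 88.9 / 94.2 | 86.3 / 92.4 | 83.7 / 90.5 | 76.1 / 84.3 |

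Simulation with six callers (20,000 runs) gave 76.7/84.1% at ICC .02 and 66.0/74.4% at ICC .05, close to the Satterthwaite rows.

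**Step 4: where the stated figure is lost.** Power at f = .09 falls below 80% once the ICC exceeds:
- .004, .009, .013 or .018 for 4, 5, 6 or 7 callers with Satterthwaite df;
- .019, .024, .029 or .034 by normal approximation.

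**The case against.** A reader might infer that the trial is underpowered, or that the design cannot deliver its stated power. The documents do not support that, for these reasons:

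- **No ICC is given.** On the stated inputs the plan understates independent-participant power by about 9 and 4 points. That margin roughly covers an ICC of .01 with six callers, or about .02 by normal approximation. Caller training is standardised, which argues for a small ICC; the calls are otherwise largely unscripted, which argues the other way.
- **Callers may be fixed effects.** Testing for differences between six named-in-advance callers at level 2 can be read that way. With inference limited to those callers, power for an equally weighted average effect is about 89% and 94% on 243 df, and the penalty above does not apply in this form. The wording about shared callers also fits random effects, so the text leaves the matter open.
- **Part of the loss comes from the df method.** With six callers and ICC 0, Satterthwaite df alone lower power from 88.7/94.1% to 85.5/91.8%. This is why both methods are shown. With so few clusters the normal approximation is the optimistic one, and the simulation sides with the df-based figures.
- **The extreme caller counts fit the plan less well.** Panels of 20 to 25 imply 125/25 = 5 to 125/20 ≈ 6 callers. Four callers would carry 31 each and seven would carry 18.

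A reader might also infer that the analysis ignores clustering. It does not, since Data Analysis commits to accounting for shared callers. The gap is in the sample-size justification.

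These points stand and limit the size of the concern. They do not remove the omission. The margin is not described as a clustering allowance, and it could equally be an unstated allowance for dropout. With 200 analysed it is already used up before any clustering.

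**Conclusion.** The concern holds in a conditional form. Two things are certain from the text: the power statement omits a source of variance that the same section expects, and its 80% and 90% do not follow from its inputs, which give 88.7% and 94.1% two-sided.

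The size of any shortfall is not certain. It rests on random caller effects and an assumed ICC. With six callers, power is close to the stated figures at ICC .01. At ICC .02 it is about 3 to 5 points short with few-cluster df and roughly as stated by normal approximation. At ICC .05 it is short for every caller count from 4 to 7 under both methods: 52% to 76% at f = .09 and 60% to 84% at f = .10.

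Severity is moderate: a figure the trial relies on needs restating, but neither the sample size nor the commitment to model shared callers is shown to be wrong.

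**What to change.** Keep 125 per arm. In Data Analysis and in the Total Sample Size table:

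1. Correct the pairing of f with power, or state the further assumption (such as dropout or a different correlation) that produces it. State that the test is two-sided, if that is intended.
2. Reconcile the caller count (4 to 6, six, or seven) and give the expected panel sizes.
3. State that callers are random effects in the intervention arm only. Alternatively, treat them as fixed and limit the conclusion to these callers.
4. If they are random, replace the unconditional 80% to 90% with power for the partially nested design over an ICC range, for example 0, .01, .02 and .05, using a small-sample df method.

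This is a change of text with no added participants. Its cost is that the stated power becomes conditional and, over part of the range, less favourable. Spreading participants over more callers would recover some power in principle, but it should not be offered as a ready remedy: callers are still being recruited, and seven would fall below the planned panel size.
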